1.0 Study Summary

Study Title	MEND 2: Making Treatment Decisions Using Genomic Testing
Study Design	Single Arm Feasibility and Efficacy Study
Primary Objective	
• Examine intervention feasibility via patient and oncologist acceptability, recruitment and retention, and fidelity
Secondary Objective(s)	
• Evaluate intervention effects on comprehension and treatment preferences.• Assess potential intervention mechanisms on comprehension, preferences, and satisfaction.
Research Intervention(s)/Investigational Agent(s)	Two surveys and audio recordings of patient-physician encounter using the question prompt list.
IND/IDE #	N/A
Study Population	Patients
Sample Size	75
Study Duration for individual participants	About a month, depending on appointment schedule.
Study Specific Abbreviations/Definitions	QPL: Question Prompt List HER2: Human Epidermal Growth Factor Receptor 2 ER: Estrogen Receptor PR: Progesterone Receptor LCCC: Lombardi Comprehensive Cancer Center WHC: Cancer Institute at Washington Hospital Center MCC: H. Lee Moffitt Comprehensive Cancer Center

2.0 Objectives*

2.1 Specific Aims.

- Specific Aim 1: Examine intervention feasibility in 3 areas: 1) patient and oncologist acceptability, 2) participant recruitment and retention, and 3) intervention dosage and fidelity.
- Specific Aim 2: Evaluate intervention effects on comprehension and treatment preferences.
- Specific Aim 3: Assess potential intervention mechanisms on comprehension, preferences, and satisfaction.

2.2 Hypotheses/Research questions.

- Aim 2 Hypothesis: Participants will demonstrate significant increases in comprehension about their disease and its treatments from pre- to post-QPL. Participants will be more likely to report Score-concordant preferences from pre to post-QPL.
- Aim 3 Hypothesis: Patient comprehension and satisfaction will be higher following encounters with greater shared decision making, greater perceived communication quality, and more frequent discussion of risks/benefits of treatments. Patient preferences will likely be more Score-concordant following encounters with greater shared decision making, greater perceived communication quality, and more frequent discussion of risks/benefits of treatments.

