3.0 Background*

Breast cancer is the most common cancer among US women, with more than 230,000 new diagnoses and 40,000 deaths each year,¹ along with decrements in quality of life.² Half of all newly-diagnosed patients are affected with estrogen-receptor positive, early-stage disease. Clinical guidelines for these women integrate genomic tumor profiling tests such as the Oncotype DX® Recurrence Score to refine recurrence estimates and systemic therapy selection when combined with existing markers. Thousands of women receive testing each year.³⁻⁵ While these women should all receive hormonal therapy, guidelines suggest that the 25% with a high Score benefit from additional chemotherapy and the 50% with a low Score can safely avoid chemotherapy.⁶ Appropriate treatment for the 25% of women with intermediate Recurrence Scores remains unclear until clinical trial (TAILORx) results are released in the next year.⁷

Despite continuing dissemination, many challenges remain to maximize the benefits offered by testing and refined treatment selection. Many women have a poor understanding of their

PROTOCOL TITLE:
Making Treatment Decisions Using Genomic Testing

Recurrence Score and its impact of treatment selection.⁸ Further, our data suggest that patients' pretesting preferences do not shift following the receipt of their Recurrence Score, even following discussion of test results that should guide treatment selection. These preferences are a powerful driver of treatment utilization, predicting treatment received over and above the effect of the Recurrence Score and other clinical variables. Indeed, many patients do not receive Score-concordant care.^{4,9-11} Finally, tested patients who do not take an active role in their care and report poorer communication by their oncologist are at risk for higher distress and poorer quality of life.¹² Our data suggest a need to test interventions that support communication about the Recurrence Score, improving patient comprehension and better aligning patient preferences with evidence-based recommendations, ultimately impacting patient morbidity and mortality. TAILORx results will continue to strengthen the evidence for clinical utility and increase testing rates. An effective intervention should be ready to respond to this increasing need.

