Street et al.'s model of patient-centered communication¹³ suggests pathways through which clinical communication has indirect effects on morbidity and mortality. Communication can influence more proximal outcomes, including patient comprehension of their disease and its treatments, treatment preferences and satisfaction, involvement in care decisions as well as longer-term outcomes of treatment adherence and quality of life.¹⁴ We aim to test the feasibility and impact of a patient activation intervention to support effective integration of the Recurrence Score into clinical encounters and treatment decisions. Patient activation interventions utilizing a question prompt list (QPL) can impact proximal outcomes of preferences, comprehension, satisfaction and involvement.¹⁵⁻¹⁸ A QPL could allow tested patients to better understand the rationale for their oncologist's treatment recommendation and its impact on the management of their disease, as well as encourage alignment of treatment preferences, the Recurrence Score and treatment selection. In this trial, we will recruit newly-diagnosed breast cancer patients to a single-arm trial to demonstrate feasibility and preliminarily assess the impact of the QPL on key outcomes.

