17.0 Data Management* and Confidentiality

17.1 We will calculate descriptive and frequency distributions for all variables. We will assess the quality of the data and evaluate the extent and impact of missing data. For categorical variables, we will use Chi-Square tests or Fisher's exact tests if needed. We will test continuous variables with Student t-tests or Mann-Whitney U tests for non-normal data. Any variable that exhibits a $p < .10$ association with the key predictors or outcomes will be controlled in multivariable analyses. Potential covariates include sociodemographic and clinical variables as well as differenced.

Our primary endpoint is the percentage of patients activated via a question prompt list intervention. Women will demonstrate significant increase in comprehension from pre- to post-QPL.

Using a 2-tailed $\alpha = 0.05$ and assumed a minimum of 75 participants at T2 and accounting for clustering by oncologist, we calculated effective sample sizes assuming an average cluster size of 10 patients per oncologist and an ICC of 0.02. This reduces the sample size by a factor of 1.18, leaving an effective $N = 64$ at T2. We will have 80% power to detect changes in mean comprehension of 0.4 SD assuming a correlation of 0.5 between pre- and post- scores. We will use multilevel models to address the clustering of observations within patients and of patients within oncologists. These mixed effects regression models will include random effects for patient and oncologist and fixed effects for time, the main predictor, and covariates. The multilevel model for 2a will be a linear model and we will estimate the adjusted mean change in comprehension and the corresponding 95% confidence interval. We will estimate an adjusted odds ratio with the corresponding 95% confidence interval.

17.2 Data collected in this study will be used exclusively for research purposes; it will be managed and stored according to our sites' security standards for data that require the highest possible security to ensure there will be no inadvertent disclosure. Any computers storing or accessing data collected for the study will be required to comply with these standards.

During the trial, all study data downloaded from REDCap or gathered from other sources will reside in a HIPAA-compliant study folder. Access to the study folder is provided based

PROTOCOL TITLE:

Making Treatment Decisions Using Genomic Testing

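### A single pooled test of Score-concordant preference cannot tell alignment with the Score from a general drift away from chemotherapy, and can mask falling concordance in high-Score women

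*Combined protocol and SAP*

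**What the plan says.** Section 2.2, Aim 2, makes one statement covering every participant: "Participants will be more likely to report Score-concordant preferences from pre to post-QPL". Aim 3 uses the same outcome: "Patient preferences will likely be more Score-concordant following encounters with greater shared decision making".

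Section 17.1 describes mixed models with random effects for patient and oncologist and fixed effects for time, a main predictor and covariates. For what appears to be the binary outcome it says only "We will estimate an adjusted odds ratio with the corresponding 95% confidence interval". It names no Score stratum and no time-by-Score term.

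Section 3.0 says guidelines suggest that "the 25% with a high Score benefit from additional chemotherapy and the 50% with a low Score can safely avoid chemotherapy". It puts intermediate Scores at 25% and treats the right choice for them as not yet settled. The same section says a question prompt list (QPL) could "encourage alignment of treatment preferences, the Recurrence Score and treatment selection".

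Section 6.4 scores preference as pros minus cons, with positive values favouring chemotherapy. It then defines preference concordance by comparing the post-Score preference with the treatment actually received, not with the Score. Under 6.2 the T1 interview comes before the Score is known. There is no comparison arm.

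**The concern.** Alignment with the Score means that high- and low-Score women diverge after T1: the former move toward chemotherapy, the latter away from it. A pooled percentage concordant does not measure that divergence. It adds a movement in one direction among low-Score women to a movement in the other direction among high-Score women, weighted by how many of each are enrolled. With twice as many low as high Scores, women who all become equally warier of chemotherapy produce a net gain. With no control arm, the drift cannot be subtracted.

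Two conclusions are at risk. A reported gain in Score concordance may contain no alignment. A pooled gain may also sit alongside high-Score women moving away from the choice that section 3.0 links to their Score. A main effect of Score among the covariates does not help, because it does not let the change over time differ by Score group.

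**Working it through.** **The plan's own figure.** Section 17.1 assumes "an average cluster size of 10 patients per oncologist and an ICC of 0.02". Design effect = 1 + (10 − 1) × 0.02 = 1.18, and 75 / 1.18 = 63.6, which reproduces the stated effective N of 64. The power statement attached to it concerns comprehension; none is given for preference concordance.

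**Inputs from the documents.** At least 75 women at T2; 50% low, 25% high, 25% intermediate (3.0). Expected numbers are 0.50 × 75 = 37.5 low and 0.25 × 75 = 18.75 high, taken as 37 and 19. On the effective N they are 32 and 16.

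**Assumptions.** Concordance is judged against the Score (low: no chemotherapy; high: chemotherapy). Intermediates are left out. Baseline preference and shift sizes are assumed, as the documents give neither.

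**Identity.** Let dL and dH be the drops in the proportion preferring chemotherapy, and wL and wH the Score shares. Low-Score concordance rises by dL and high-Score concordance falls by dH, so

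pooled change = (wL·dL − wH·dH) / (wL + wH).

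- Uniform drop d: (0.50 − 0.25) / 0.75 × d = d/3. A 10-point drop gives +3.3 points pooled, while low-Score concordance rises 10 and high-Score concordance falls 10.
- Sign: positive when dH < 2·dL. With dL = 20 and dH = 40 the pooled change is exactly zero.
- Intermediates counted as no-chemotherapy: (0.75 − 0.25) / 1.00 = 0.5, or +5 points per 10. Counted as chemotherapy: (0.50 − 0.50) / 1.00 = 0.

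**Chance of a significant pooled gain with no alignment.** Simulation with 37 low and 19 high, correlated binary preferences (latent T1–T2 correlation 0.5), a two-sided 5% McNemar-type test, and no oncologist clustering. The pooled change is (37 − 19)/56 = 0.321 of the drop.

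| Uniform drop | Pooled change | Significant gain |
|---|---|---|
| none | 0 | about 2.5% |
| 10 points | +3.2 | about 6% |
| 20 points | +6.4 | about 12% |
| 30 points (50% to 20%) | +9.6 | about 19% |
| 40 points (60% to 20%) | +12.9 | about 26% |

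In the 40-point case the high-versus-low contrast in change is significant in the alignment direction in about 3% of trials.

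**A masked loss.** Suppose low-Score preference falls from 50% to 20% and high-Score preference from 50% to 35%. Pooled change = (37 × 30 − 19 × 15)/56 = +14.7 points, significant in about 45% of trials, while high-Score concordance falls 15 points. The contrast is −15 − (−30) = +15 points, so it too points toward alignment (significantly so in about 16%). Only results by Score category show the fall.

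**Price of the contrast.** If only low-Score women align (50% to 20%, high unchanged at 50%), the pooled test has about 74% power and the contrast about 48%. The 95% half-width for a single high-Score proportion at 50% is 1.96 × √(0.25/19) = 22 points, or 1.96 × √(0.25/16) = 25 points on the effective N.

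**The case against.** The strongest reply is that section 6.4 gives the plan's only operational definition of concordance, a match to treatment received. Under that rule the low/high weighting does not apply as described. This stands in part: the point concerns the outcome named in 2.2, and the two sections must be reconciled first. But the 6.4 definition covers only the post-Score preference, so it cannot supply the pre-to-post change that Aim 2 tests.

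Second, pooling is inferred. The odds-ratio sentence names no outcome, and the main predictor is not identified. A reader might conclude that a pooled test was deliberately chosen. The documents do not show that; they leave the analysis under-specified, and pooling is its natural reading.

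Third, a reader might infer that every general move away from chemotherapy will register as better alignment. It will not if high-Score women move at least twice as far as low-Score women, or if intermediates are counted as chemotherapy-concordant.

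Fourth, large shifts may be unlikely. Section 3.0 reports that preferences did not shift after the Score in the team's earlier data. Those data preceded the QPL and do not show what happens with it, but drops of 10 to 20 points inflate the error rate only modestly. Counting intermediates as no-chemotherapy gives much larger rates (about 57% and 77% for drops of 30 and 40 points), but section 3.0 does not support that classification.

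Finally, T1 precedes the Score and there is one arm, so even a time-by-Score contrast cannot separate the QPL from Score disclosure. That is true, and it limits any causal claim. It does not make the pooled figure a measure of alignment.

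**Conclusion.** The concern holds in a bounded form. If Aim 2 concordance is judged against the Score, intermediates are left out and one odds ratio is reported, a third of any uniform drop in chemotherapy preference appears as improved concordance. A pooled gain can then reflect drift, or conceal a loss in high-Score women, whenever the high-Score drop is less than twice the low-Score drop. The direction follows from the 2:1 mix in section 3.0. The chance of a falsely significant gain, about 6% to 26% for drops of 10 to 40 points, rests on assumed shifts, an assumed correlation and no clustering.

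A reader might go further and treat this as a flaw that must be repaired before the trial can proceed. The documents do not support that: the primary objective is feasibility, intervention effects are secondary and described as preliminary, and no power is claimed for preferences. It is a should-fix, because it determines what the trial can say about alignment.

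**What to change.** 1. Reconcile 2.2 with 6.4 so that the Aim 2 preference outcome is concordance with the Score. If agreement with treatment received is also wanted, give it a separate name.
2. State that intermediate Scores are left out of that outcome, since section 3.0 gives no settled concordant choice for them.
3. In 17.1, always report the change in chemotherapy preference and in concordance separately for low- and high-Score women, with 95% confidence intervals. This must be unconditional, because the contrast alone can miss a loss in high-Score women.
4. Add the time-by-Score-category estimate (high versus low). Claim alignment only if that contrast supports it, not from the pooled odds ratio alone.
5. Report the Aim 3 preference results by Score category in the same way.

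This changes wording only; Score category and T1/T2 preferences are already collected. The price is precision. About 19 high-Score women give intervals of roughly ±22 to 25 points on a proportion, so the by-category results are descriptive. The contrast is also weaker than the pooled test when only low-Score women align (about 48% against 74% in the case worked above).

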3.0 Background*

Breast cancer is the most common cancer among US women, with more than 230,000 new diagnoses and 40,000 deaths each year,¹ along with decrements in quality of life.² Half of all newly-diagnosed patients are affected with estrogen-receptor positive, early-stage disease. Clinical guidelines for these women integrate genomic tumor profiling tests such as the Oncotype DX® Recurrence Score to refine recurrence estimates and systemic therapy selection when combined with existing markers. Thousands of women receive testing each year.³⁻⁵ While these women should all receive hormonal therapy, guidelines suggest that the 25% with a high Score benefit from additional chemotherapy and the 50% with a low Score can safely avoid chemotherapy.⁶ Appropriate treatment for the 25% of women with intermediate Recurrence Scores remains unclear until clinical trial (TAILORx) results are released in the next year.⁷

Despite continuing dissemination, many challenges remain to maximize the benefits offered by testing and refined treatment selection. Many women have a poor understanding of their

PROTOCOL TITLE:
Making Treatment Decisions Using Genomic Testing

Recurrence Score and its impact of treatment selection.⁸ Further, our data suggest that patients' pretesting preferences do not shift following the receipt of their Recurrence Score, even following discussion of test results that should guide treatment selection. These preferences are a powerful driver of treatment utilization, predicting treatment received over and above the effect of the Recurrence Score and other clinical variables. Indeed, many patients do not receive Score-concordant care.^{4,9-11} Finally, tested patients who do not take an active role in their care and report poorer communication by their oncologist are at risk for higher distress and poorer quality of life.¹² Our data suggest a need to test interventions that support communication about the Recurrence Score, improving patient comprehension and better aligning patient preferences with evidence-based recommendations, ultimately impacting patient morbidity and mortality. TAILORx results will continue to strengthen the evidence for clinical utility and increase testing rates. An effective intervention should be ready to respond to this increasing need.

Street et al.'s model of patient-centered communication¹³ suggests pathways through which clinical communication has indirect effects on morbidity and mortality. Communication can influence more proximal outcomes, including patient comprehension of their disease and its treatments, treatment preferences and satisfaction, involvement in care decisions as well as longer-term outcomes of treatment adherence and quality of life.¹⁴ We aim to test the feasibility and impact of a patient activation intervention to support effective integration of the Recurrence Score into clinical encounters and treatment decisions. Patient activation interventions utilizing a question prompt list (QPL) can impact proximal outcomes of preferences, comprehension, satisfaction and involvement.¹⁵⁻¹⁸ A QPL could allow tested patients to better understand the rationale for their oncologist's treatment recommendation and its impact on the management of their disease, as well as encourage alignment of treatment preferences, the Recurrence Score and treatment selection. In this trial, we will recruit newly-diagnosed breast cancer patients to a single-arm trial to demonstrate feasibility and preliminarily assess the impact of the QPL on key outcomes.

4.0 Study Endpoints*

- 4.1 *Primary Endpoint:* Patient activation via a question prompt list intervention.
- 4.2 *Secondary Endpoints:* ____.
- 4.3 *Safety Endpoints:* Safety endpoints have not been established as this is a minimal risk study.

5.0 Study Intervention/Investigational Agent

N/A

6.0 Procedures Involved*

PROTOCOL TITLE:

Making Treatment Decisions Using Genomic Testing

6.1 This is a feasibility and efficacy study. Two participant interviews will be conducted by the study staff. Audio recordings will be collected of patient-physician encounters using the QPL over a month time span.

6.2 Eligible patients will be contacted by study staff via phone call. The study staff will describe the study, answer questions, obtain verbal consent, and complete the first, T1 interview before the patient receives *Oncotype DX* results. After obtaining a signed informed consent and HIPAA authorization by mail, the QPL will be provided to the patient. They will receive the QPL by mail or email, depending on their preference, before their Score disclosure appointment. Study staff will be available to audio record the patient-physician encounter during their appointment. The second, T2 interview will be done after patients receive their test results but prior to initiation of adjuvant chemotherapy.

6.3 The risks of participation are minimal. The survey elements have been designed to minimize emotional distress. A distress protocol has been put in place to refer subjects to psychological consult when appropriate. It is possible that participants will derive benefit from the use of the QPL in how they communicate with their physician and make decisions regarding treatment options.

6.4 Measures will include:

Sociodemographics. We will assess age, race/ethnicity, education, marital, employment, income, insurance status, comorbidity, and family cancer history.

Disease variables and treatments. We will assess diagnosis date, pathology (staging, grade, ER/PR/HER2), treatments, and dates.

Oncotype DX Recurrence Score. We will assess the Recurrence Score and the related category.

Chemotherapy Selection. In our work, 95% of women make definitive treatment decisions by T2. If not, this will be noted and the interview will continue. *Data will be confirmed in the medical record.*

Self-Reported Measures:

Table 1. Variables and Data Sources		Timepoint		
Variable	Measure/source	T1	Encounter	T2
Controlling and Clinical Variables				
Sociodemographics		X		
Disease Variables, Treatments	Self-report and chart review	X		X
Recurrence Score	Self-report and chart review			X
Outcomes and Mediators				
Chemo. Selection	Self-report and chart review			X

PROTOCOL TITLE:
Making Treatment Decisions Using Genomic Testing

Chemo. Preferences	Preferences	X		X
Comprehension	Adjuvant treatment, Recurrence Score, treatment implications	X		X
Coding of clinical encounters	RS- and treatment related information, shared decision making, patient active participation and patient-centered communication		X	X
Decisional Satisfaction	SDS			X
Communication Quality	Makoul et al.			X

Chemotherapy Preferences. We will assess preferences for chemotherapy by assessing the perceived pros (8 items) and cons (8 items) of treatment as we do in our ongoing work. Women rate the importance of each item on a scale from 1 (*Not at all important*) to 4 (*Very important*). Ratings are averaged to create scales, with higher scores indicating greater importance of pros and cons. Internal reliability is high for pros-cons, with scores above zero indicating a preference for chemotherapy. Preference concordance will be determined through a match between post-Score preference and treatment received.

Comprehension. We will assess comprehension of adjuvant treatment, Recurrence Score and category, and treatment implications (*The Test helps women decide about chemotherapy (Y/N)*). We will apply existing comprehension items, in which patients average 70% correct.¹⁴

Satisfaction. We will assess Decisional Satisfaction with the valid and reliable 6-item Satisfaction with Decision Scale, rated on a 5-point Likert scale (*Strongly agree/ disagree*), with a higher score indicating greater satisfaction. The measure has been used to assess satisfaction with breast cancer adjuvant treatment decisions.¹⁹

Perceived communication quality. We will assess patients' perceptions of quality of patient-physician communication using a 7-item scale from 1 (*Very strongly disagree*) to 6 (*Very strongly agree*). This scale has good reliability and validity and we have used this measure in our current observational study. Items are relevant to chemotherapy decisions (*The doctor fully explained the risks of treatment recommended*). Patients will respond to these regarding their primary Medical Oncologist.²⁰

Oncologist variables. We will record race, ethnicity, and gender of the patient's primary medical oncologist for our measurement of concordance.

Coding of Oncology Encounters. We will audio record, transcribe, and code clinical encounters to inform potential intervention mechanisms. Broadly speaking, coding systems capture an encounter's content and process. No single coding system has emerged as definitive or captures our specific encounter content and communication processes. We will code encounters for RS- and treatment related information, shared decision making, patient active participation and patient-centered communication.^{21,22} [name] will merge these data with patient self-report using study ID.

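### The Aim 2 preference hypothesis appears to be tested only on a score cut at zero; adding a signed continuous analysis would recover about half the information or more, at almost no cost

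*Combined protocol and SAP*

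**What the plan says.** **Measure.** Section 6.4 (Chemotherapy Preferences) has 8 pros and 8 cons items, each rated 1 to 4 and averaged within its scale. The difference, pros minus cons, is interpreted "with scores above zero indicating a preference for chemotherapy". Table 1 schedules preferences at both T1 and T2.

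**Hypothesis.** Section 2.2, Aim 2: "Participants will be more likely to report Score-concordant preferences from pre to post-QPL".

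**Analysis.** Section 17.1 assigns a linear multilevel model to the outcome it calls 2a, with an adjusted mean change in comprehension. It then adds "We will estimate an adjusted odds ratio with the corresponding 95% confidence interval" and does not say for which outcome. An odds ratio needs a binary outcome, and preference concordance is the only Aim 2 outcome left, so that is the natural reading.

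**Power.** The only statement concerns comprehension: "We will have 80% power to detect changes in mean comprehension of 0.4 SD", "assuming a correlation of 0.5 between pre- and post- scores". No baseline concordance, expected change or power is given for preferences.

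**Definition of concordance.** Section 6.4 defines it as agreement between the preference after the Score and the treatment the patient received. Section 2.2 speaks of agreement with the Score, before and after the QPL.

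**The concern.** With eight items on each side, all answered, the difference runs from -3 to +3 in steps of 1/8. Cutting it at zero keeps only the sign. A low-Score patient who moves from +1.000 to +0.125 has come most of the way toward the Score-indicated option and counts as unchanged. One who moves from +0.125 to 0 has shifted one item by one point and counts as a full change. A score of exactly zero is not above zero, so an evenly balanced low-Score patient is classed as concordant by default.

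At stake is the sensitivity of the second Aim 2 hypothesis. Section 3.0 reports that, in the team's own data, preferences did not move after the Score was received. If the only analysis described has low power, the trial may say little about whether that holds here, although the data collected could say more.

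**Working it through.** **1. The plan's own figure (comprehension).** Inputs from section 17.1: "Using a 2-tailed $\alpha = 0.05$ and assumed a minimum of 75 participants at T2"; "assuming an average cluster size of 10 patients per oncologist and an ICC of 0.02"; correlation 0.5.
- Design effect = 1 + (10 - 1) × 0.02 = 1.18, and 75/1.18 = 63.6, which agrees with "leaving an effective $N = 64$ at T2".
- SD of change = SD × √(2(1 - 0.5)) = 1.0 SD.
- Power of a paired t test at 0.4 SD with n = 64 is 88%. The change detectable with 80% power is 0.356 SD. The plan's 80% at 0.4 SD is therefore conservative and is not a problem for this point.

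**2. Patients with a Score-indicated option.** Section 3.0 gives 50% low, 25% high and 25% intermediate, and says that appropriate treatment is unclear for the last group. Low plus high: 0.75 × 75 = 56. With the design effect: 0.75 × 64 = 48.

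**3. Assumptions not in the documents for preferences.** The T1 and T2 scores, signed toward the Score-indicated option, are bivariate normal with equal SD. The correlation of 0.5 and the 0.4 SD shift are borrowed from comprehension. T1 concordance is 50% or 69%; neither has a source in the protocol. Two-sided alpha is 0.05.

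**4. Information kept by the cut.** For small shifts, relative efficiency = φ(a)² × 2(1 - ρ) / p_d. Here a = Φ⁻¹(T1 concordance), and p_d is the proportion changing class when there is no shift.
- T1 concordance 50%: φ(0)² = 0.159 and p_d = 1/3, giving 0.159 × 1.0 / 0.333 = 0.48.
- T1 concordance 69%: p_d = 0.291, giving 0.43.

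The cut analysis of 56 patients is thus worth about 0.48 × 56 = 27, or 0.43 × 56 = 24, patients analysed on the uncut score.

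**5. Power, worked case (n = 56, 0.4 SD, 50% concordant at T1).**
- Uncut: noncentrality 0.4 × √56 = 2.99 on 55 df, power 83.7%.
- Cut: T2 concordance Φ(0.4) = 0.655. The probability of becoming concordant is 0.251 and of ceasing to be so 0.096. About (0.251 + 0.096) × 56 = 19 patients carry all the evidence. McNemar power is 43.1% (exact), 50.5% (mid-p) or 52.8% (uncorrected).

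**6. Other cases.** Power in %; each cut range runs from the exact to the uncorrected McNemar test.

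| n | Shift | Uncut | Cut, 50% at T1 | Cut, 69% at T1 |
|---|---|---|---|---|
| 56 | 0.3 SD | 59.7 | 25.2-33.5 | 20.6-27.7 |
| 56 | 0.4 SD | 83.7 | 43.1-52.8 | 34.6-43.4 |
| 56 | 0.5 SD | 95.7 | 62.2-71.1 | 50.4-59.5 |
| 48 | 0.4 SD | 77.5 | 36.7-45.7 | 28.4-36.9 |

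Cut power as a share of uncut power at n = 56 is 0.35-0.56 at 0.3 SD, 0.41-0.63 at 0.4 SD and 0.53-0.74 at 0.5 SD.

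McNemar's test stands in here for the planned mixed logistic model. That model would give similar but not identical figures.

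**The case against.** **The binary-only analysis is inferred.** This stands. The odds-ratio sentence names no outcome, and the zero point in section 6.4 interprets the scale without excluding other uses. A reader might infer that the plan chose to discard the continuous score. It does not say so; it simply describes no analysis of it.

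**The hypothesis is itself binary.** This also stands. A low-Score patient moving from -0.5 to -1.5 was concordant and remains so, and counting no change is right for the question as worded. A signed mean can rise without one more patient becoming concordant. The continuous score answers a neighbouring question and should not displace the odds ratio.

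**Power is not simply halved.** A reader might infer a halving from the loss of half the information. At 50% T1 concordance and 0.4 SD with n = 56, the uncorrected test keeps 52.8/83.7 = 63% of the power. A halving needs T1 concordance near 70%, a smaller shift or the conservative exact test. The shift and correlation belong to comprehension, and the baseline rates are assumed.

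**A null would not necessarily be misread.** The promised 95% confidence interval would show the imprecision. Feasibility is the primary objective, and section 3.0 describes the assessment of impact as preliminary. The documents do not support saying that a non-significant result would be reported as evidence of no shift.

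**More power would not show a QPL effect.** T1 precedes and T2 follows Score disclosure in a single arm. Neither analysis can separate the QPL from the Score itself.

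What these objections leave intact is that a more sensitive analysis of data already scheduled is missing from the plan.

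**Conclusion.** The point holds as a cheap improvement to a secondary aim. Under the stated assumptions, the cut discards about 52% of the information at 50% T1 concordance and 57% at 69%. At a 0.4 SD shift, power falls from about 84% to 35-53% with 56 patients, or from about 77% to 28-46% with the plan's clustering allowance. The relative loss is smaller for larger shifts: at 0.5 SD with 56 patients, about 96% falls to 50-71%. These figures illustrate the size of the loss and do not contradict any stated figure, because the protocol gives no power for this hypothesis.

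The mismatch between the two definitions of concordance is more basic. Until it is resolved, even the binary outcome is not fixed.

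**What to change.** In sections 6.4 and 17.1:

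1. Name Score concordance as the outcome of the adjusted odds ratio, and keep it because it matches the hypothesis as worded.
2. Add a pre-specified analysis of T1-to-T2 change in the continuous score, signed toward the Score-indicated option: pros minus cons for high-Score patients, cons minus pros for low-Score patients. Use the linear mixed model already planned for comprehension.
3. Describe intermediate-Score patients separately, since section 3.0 gives no settled option against which to sign their score.
4. State how a score of exactly zero is classified.
5. Reconcile the definition in section 6.4 (preference after the Score against treatment received) with that in section 2.2 (preference against the Score, before and after). If both are wanted, give them different names.

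The cost is a few sentences and one further analysis, with no new data. The added result is in scale points, which are harder to communicate than a percentage; the retained odds ratio covers that. It remains a pre-post change and should be reported as such.
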